7.2. Key Definitions

7.2.1. Clinically Symptomatic Respiratory Illness (CSRI)

A CSRI is defined as the occurrence of:

- a. At least 2 respiratory symptoms (runny nose/sneezing [considered one symptom], stuffy nose, sore throat, hoarseness, or cough) OR 1 respiratory symptom and 1 of the following general symptoms (headache, feverishness/chills or loss of appetite),

AND

- b. at least 1 of these respiratory symptoms (runny nose, sneezing, stuffy nose, sore throat, hoarseness or cough) in (a) above being reported on 2 or more “consecutive entries” in the eDiary, and must
 - i. overlap with another respiratory or general symptom for at least 1 day, or
 - ii. be reported on a consecutive day to another respiratory or general symptom in the eDiary

AND

- c. any 2 or more symptoms (respiratory and/or general) reported during the CSRI event that are at least moderate in severity.

All CSRI-defining symptoms (i.e., runny nose, sneezing, stuffy nose, sore throat, hoarseness, cough, headache, feverishness/chills or loss of appetite) that occur after the start of a CSRI event will be included as part of a single CSRI event unless there is a period of ≥ 7 consecutive entries during which all CSRI-defining symptoms are reported as “Absent” in the eDiary.

“consecutive entries” include situations in which eDiary entries were missing for 1-6 days in between 2 days in which the symptom was reported. For example, if on Day 3 and Day 9 runny nose was reported but eDiary entries were missing from Days 4-8, then runny nose will be considered as reported for 2 consecutive entries. This definition of “consecutive entries” does not include situations in which subjects report all symptoms as “Absent”. If ≥ 7 days of eDiary entries are missing, then symptoms reported before and after the ≥ 7 days of missing entries will not be considered consecutive eDiary entries.

The start date of the CSRI will be the start date of the first respiratory symptom reported as part of the CSRI. Note that the start date of a CSRI will always be based on the start date of the respiratory symptom and not a general symptom.

This document is confidential.

The end date of the CSRI will be defined as the latest date that any of the CSRI-defining symptoms for the same CSRI event were reported.

A separate CSRI event will not be diagnosed until a subject has ≥ 7 consecutive days during which all CSRI-defining symptoms are reported as “Absent” after the end date of the prior CSRI episode. If missing days of eDiary entries are sandwiched between 2 days of eDiary entries during which all CSRI-defining symptoms are reported as “Absent”, then all symptoms will also be considered as “Absent” for the missing eDiary entries, and a separate CSRI event can be diagnosed if the ≥ 7 consecutive days criterion is met. For example, if on Day 4 and Day 10 all symptoms were reported as “Absent” in the eDiary, and on Days 5-9 the eDiary entries were missing, then all symptoms will be considered as “Absent” on Days 5-9. Therefore all symptoms will be considered as “Absent” for 7 consecutive days (Days 4-10), and a separate CSRI can be diagnosed.

Only CSRI events having a start date at least 3 days after the start of study drug and meet the definition of a CSRI by the specified time point (Week 16 or Week 20) will be included in the analysis. Only data recorded in the eDiary through the evening before the Week 16 visit will be included in all analyses of CSRI events for the Week 16 endpoint. Similarly, only data recorded in the eDiary through the evening before the Week 20 visit will be included in all analyses of CSRI events for the Week 20 endpoint.

7.2.2. First Dose Date

For any randomized subject, if there are any entries in the eDiary indicating the subject took study drug at any time during the study, then the first dose date will equal the randomization date because all subjects receive their first dose of study drug at the site during the Baseline (randomization) visit. However, if there are no entries in the eDiary indicating the subject took study drug at any time during the study (including at the Baseline visit), then the first dose date will be missing and the subject will be considered randomized but not treated.

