Subjects will be treated for 16 weeks with study drug. Approximately 533 subjects will be enrolled in each treatment group for a total enrollment of approximately 1066 subjects.

Baseline Visit

At the Baseline visit, a review of any changes to the subject's medical (including cardiac) condition or current medications/other therapies will be performed. Subjects will then undergo clinical evaluation, including a targeted physical exam. This should include measurements of weight and vital signs, including orthostatic blood pressure, and an exam of the lungs, heart, oral cavity, and skin. The Clinical Frailty Scale (see [Section 13.4](#) [Appendix 4]) score of each subject will also be determined. An ECG will be performed for Baseline safety assessment. Subjects will also have blood and urine samples obtained for Baseline safety assessments. In addition, blood samples will be obtained for biomarker analyses, including RNA expression and soluble biomarkers. Consent for Optional Blood Storage for Future Use and Consent for Optional Pharmacogenetic Analysis will be obtained at the Baseline Visit. A single blood sample will also be obtained at the Baseline Visit in those subjects who sign the option Pharmacogenetic Analysis consent form for the purposes of possible future Pharmacogenomic analysis. A mid-turbinate nasal swab specimen will be collected.

Prior to randomization, the inclusion and exclusion criteria will be reviewed again, and eligible subjects will be randomized via the IXRS system to 1 of 2 treatment groups in a ratio of 1:1.

- RTB101 10 mg once daily (QD)
- Matching placebo QD

Randomization will be stratified based on the following factors that may influence the incidence or severity of clinically symptomatic respiratory illness and/or the response to RTB101 treatment:

1. Age \geq 85

2. Age ≥ 65 and < 85 years with a medical history of asthma
3. Clinical Frailty Scale score ≥ 4

Subjects will be given their first dose of study drug (and time of dosing recorded in the eDiary) at the study site and trained on use of the eDiary containing study assessments to be completed at home including:

- Study drug dosing information, to be completed daily through the Week 16 study visit
- Respiratory Illness Symptom Questionnaire, to be completed daily in the evening through the Week 20 study visit
- EQ-5D-5L, to be completed each day subjects report experiencing one or more respiratory illness symptoms through the Week 16 study visit

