¹¹ All subjects will be administered their first dose of study drug at the site at the Baseline Visit. Approximately 400 subjects (per IXRS randomization) will be required to undergo PK assessment in the study (~ 200 from each treatment arm). For subjects participating in the PK analysis for the study, at the Week 4 (or Week 6 if applicable) and Week 12 study visits, study drug should not be taken at home and instead study drug will be administered together with a light meal at the study site following the pre-dose PK draw. If PK sampling cannot be performed at the Week 4 visit for logistical reasons, it should be collected at the Week 6 visit instead, but according to the schedule described above for Week 4. This applies to timing of biomarker samples originally scheduled for Week 4 as well.

^{12a} Subject will be given a personal tablet device containing the eDiary and instructions on use at this visit.

^{12b} The personal tablet device containing the eDiary will be collected from the subject at this visit.

¹³ Health Related Quality of Life (EQ-5D-5L) to be completed by all subjects at Baseline and Week 16, and each day that they report experiencing one or more respiratory illness symptoms through Week 20.

¹⁴ Nasopharyngeal swabs for respiratory pathogen PCR is to be done during a scheduled or an unscheduled visit for all subjects who report at least one unique respiratory symptom (runny nose, sneezing, stuffy nose, sore throat, hoarseness, or cough) on 2 consecutive entries in their eDiary. The swabs should be obtained if they are able to within 48 hours of 2 consecutive eDiary entries of one or more unique respiratory symptoms. Subjects who record at least 1 respiratory symptom and at least 1 general (headache, feverishness/chills or loss of appetite) symptom, both of which are moderate or severe on two consecutive days in their eDiary, should be brought in within 24 hours of the second day of eDiary symptom entry. Subjects who are unable to come to the study site may also have the nasopharyngeal swab (and, if indicated, a sputum specimen and RIDT) obtained during a home visit by trained personnel. Only one nasopharyngeal swab should be obtained during each episode of respiratory illness. Nasopharyngeal swabs will be collected through Week 20, see the SOM for more details.

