6.5. Treatment Exposure and Compliance

Compliance will be assessed by a dosing eDiary completed by the subjects daily at home (with the exception of the Baseline visit, when it will be completed at the site). In addition, compliance will be assessed at each visit by study personnel doing a pill count of remaining study drug brought by subjects to the site. All study treatment dispensed and returned must be recorded in the Drug Accountability Log.

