5.2. Safety Set

The Safety Set (SAF) will include all subjects who were administered any dose of any study drug. Subjects will be analyzed per the actual study treatment they received. The follow-up period will include the Week 20 visit which is 4 weeks after the end of the treatment period. The SAF will be used for all analyses and presentation of by-subject listings of all safety endpoints. Subjects will be analyzed according the actual treatment they received.

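### SAP 7.2.2 tests treated status by eDiary dosing entries alone, so a subject dosed at the site with no dosing entry at any time would fall out of the FAS and the Safety Set tables

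*SAP*

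**What the plan says.** SAP 7.2.2 (First Dose Date) has two branches.

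- A subject counts as treated, with the first dose date set to the randomization date, "if there are any entries in the eDiary indicating the subject took study drug at any time during the study". The stated reason is that "all subjects receive their first dose of study drug at the site during the Baseline (randomization) visit".
- In the other branch, "if there are no entries in the eDiary indicating the subject took study drug at any time during the study", and the SAP adds that this includes Baseline, "then the first dose date will be missing and the subject will be considered randomized but not treated".

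The protocol agrees that the first dose is a site event. Table 6-1, footnote 11: "All subjects will be administered their first dose of study drug at the site at the Baseline Visit". Section 3.1 adds where it is recorded: "Subjects will be given their first dose of study drug (and time of dosing recorded in the eDiary) at the study site". Section 6.5 says the dosing eDiary is filled in at home except at Baseline, when it is completed at the site.

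The analysis sets depend on administration. SAP 5.2: "The Safety Set (SAF) will include all subjects who were administered any dose of any study drug". SAP 5.3 and Protocol 9.1 define the FAS as randomized subjects who had at least one dose. Neither definition mentions the eDiary.

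Other evidence is collected. Protocol 6.5: "All study treatment dispensed and returned must be recorded in the Drug Accountability Log", and staff count the remaining capsules at visits. Protocol 8.1 requires visit notes as source documents. SAP 7.2.2 uses none of these.

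**The concern.** The rule lets a missing electronic entry override the premise in its own paragraph that every subject was dosed at the site. If it misfires, a dosed subject stays only in the Randomized Set. Three things follow.

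- **Safety tables.** The adverse event summaries run on the Safety Set, so that subject's events would not be in them. With no first dose date there is also no Study Day 1 (SAP 7.2.3), on which the treatment-emergent definition in SAP 10.3 rests.
- **Primary analysis.** SAP 7.3 already says how to score someone who leaves early: as a CSRI if the reason was an RTI adverse event, otherwise as no CSRI. The diary rule would drop the subject instead. That is an exclusion after randomization that depends on recording behaviour.
- **Departure from the protocol.** The protocol puts no diary condition on either set, and SAP section 12 does not list one among its changes.

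**Working it through.** The SAP rule states no figure, so the main check is to set the rule against the set definitions. Power is then used to gauge size.

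**1. When the rule gives a wrong answer**

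| Dosed at site? | Baseline dosing entry | Any later dosing entry | Class under SAP 7.2.2 | Correct? |
|---|---|---|---|---|
| Yes | Present | Any | Treated | Yes |
| Yes | Missing | At least one | Treated, dated to randomization | Yes |
| Yes | Missing | None | Untreated | **No** |
| No | Missing | None | Untreated | Yes |

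Only the third row fails, and it needs two things together: no Baseline entry, and no later dosing entry.

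**2. What that row loses.** An untreated subject meets neither SAP 5.2 nor SAP 5.3. SAP 7.1 puts all randomized subjects in the listings, while the index in SAP section 17 assigns the adverse event listing to the Safety Set. The listings may therefore still show the subject; the summary tables would not.

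**3. The plan's own figure.** Inputs from Protocol 9.6: 28.2% against 19.7%, two-sided alpha 0.05, 1:1 allocation, 1066 subjects, likelihood ratio chi-square test. With n per arm, p̄ = (0.282 + 0.197)/2 = 0.2395 and H(p, q) = p·ln(p/q) + (1−p)·ln((1−p)/(1−q)), the noncentrality is

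λ = 2n[H(0.282, p̄) + H(0.197, p̄)].

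At n = 533, λ is about 10.6 and power is 0.903. With an exact 30% reduction (0.7 × 28.2% = 19.74%) the same method needs 533 per arm, or 1066. The stated sample size is reproduced.

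**4. Power if the rule removes dosed subjects.** The documents give no rate, so every rate here is an assumption. The same share is removed from each arm.

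| Removed | Lost per arm | n per arm | Power |
|---|---|---|---|
| 0 | 0 | 533 | 0.903 |
| 0.5% | 3 | 530 | 0.901 |
| 1% | 5 | 528 | 0.900 |
| 2% | 11 | 522 | 0.897 |
| 5% | 27 | 506 | 0.888 |

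Losing 5, 10 or 20 subjects from the RTB101 arm only gives 0.902, 0.900 and 0.897.

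**5. Effect on the event rate.** A restored subject with no diary data would be scored as no CSRI unless the reason for leaving was an RTI adverse event. Placebo events at 28.2% are about 150 of 533, or 28.1%. Dropping 5 such non-events gives 150/528 = 28.4%.

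**The case against.** The strongest reply is that the gap is narrow and partly watched.

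- **The Baseline entry is a supervised one.** A reader might infer that someone who reacts to the first dose and leaves would be classed as untreated. The documents do not support that. The dosing entry is made at the site at Baseline (Protocol 3.1 and 6.5), so that subject should already have the one entry needed. Sites also monitor the diary and contact subjects who miss entries (Protocol 3.1).
- **The SAP rule can be read as the data test for administration.** The eDiary is source data under Protocol 8.2, and SAP 5.2 and 5.3 do not cite 7.2.2. So the definitions do not formally contradict the rule. It is an operational test that can give an answer the definitions would not.
- **Exclusions are reviewed.** Protocol 9.1 leaves final exclusions from any set to a blinded data review meeting, and SAP 8.1 has the reasons tabulated and listed. This makes a wrong exclusion visible. It does not correct it, because neither document says that other evidence may override 7.2.2.
- **Safety oversight continues.** A reader might infer that all of the subject's adverse events disappear. They do not: SAEs go to the sponsor within 24 hours (Protocol 7.2.2) and the DMC reviews SAEs unblinded (Protocol 8.4). The loss is from the Safety Set outputs.
- **The alternative sources are imperfect.** Dispensing is not ingestion. Pill counts begin at Week 2 and need the drug to come back. No separate eCRF record of the Baseline dose is identified.

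All of these points stand. They limit the frequency and shape the fix, but the written rule still gives the wrong class in the third row of the first table.

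**Conclusion.** The point holds in a limited form. SAP 7.2.2 can class a dosed subject as untreated, and so remove that subject from the FAS and the Safety Set summary tables, when the site-completed Baseline entry is missing and no later dosing entry exists.

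The number affected is unknown and probably very small. If it were 0.1% to 0.5% of subjects, that would be 1066 × 0.001 = 1.1 to 1066 × 0.005 = 5.3, or about 1 to 5 people. Nothing in the documents supports that range, and it should not be read as an estimate. Power barely moves at such rates, and no mechanism that differs by arm is shown in this double-blind trial. The planned sample size is unaffected. What matters is that set membership should follow from dosing and that the safety tables should be complete. This is a minor, worthwhile correction.

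**What to change.** Amend SAP 7.2.2 along these lines:

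- A subject with no eDiary dosing entry is classed as untreated only if the site source documentation of the Baseline visit and the pill count or accountability of returned drug also show that no dose was taken.
- Dispensing alone does not count as dosing.
- If any of these sources shows a dose at Baseline, the first dose date is the randomization date.
- Subjects whose sources disagree, or for whom a source is missing, are listed for the blinded data review before unblinding.

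The inputs are largely required already. Protocol 8.1 calls for visit notes as source documents. Protocol 5.5.2 has subjects who stop because of an adverse event come back as soon as possible to return all drug, and others return it at the next visit. Whether the Baseline notes record the dose separately from the eDiary should be confirmed with the sites.

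The cost is a short SAP amendment and source reconciliation for a few subjects. Sample size and model do not change.

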7.2.3. Study Day

Study day 1 is defined as the first dosing day of study drug. Subsequent days are numbered consecutively (Day 2, Day 3, etc.). Before the day of study drug administration, study days are numbered sequentially with negative values (i.e., Day -1, Day -2, etc.). There is no Day 0.

7.2.4. Baseline

Baseline is defined as the last measurement taken before the first dose of double-blind treatment on Day 1, unless otherwise specified.

7.3. Missing Data

Every effort will be made to collect all data at specified timepoints, according to the schedule of study events.

For the primary efficacy endpoint of occurrence of CSRI, subjects who did not meet the study definition for CSRI and discontinued the study prematurely due to a respiratory tract infection (RTI) adverse event (AE) or RTI serious adverse event (SAE) will be imputed to have experienced a CSRI; subjects who discontinued the study prematurely due to any reason aside from an RTI AE or RTI SAE and did not meet the CSRI definition will be imputed as having no CSRI; subjects who completed the study who did not meet the CSRI definition and have intermittent missing eDiary data will be imputed as having no CSRI.

This document is confidential.

Partial dates of medications will be imputed solely for the purpose of defining prior/concomitant status for medications. Dates will be defined using the hierarchy of derivations below.

- For missing start day where month and year are present, the start day will be set to the 1st of the month, unless the month and year are the same as the first dose month and year and the 1st of the month is before the first dose date, in which case, the start date will be set to the first dose date.
- For missing start day and month where year is present, the start day and month will be set to January 1st, unless the year is the same as the first dose year and January 1st is before the first dose date, in which case, the start date will be set to the first dose date.
- For missing end day where month and year are present, the end day will be set to the last day of the month, unless the month and year are the same as the trial termination month and year, in which case, the end date will be set to the trial termination date.
- For missing end day and month, where year is present, the end date will be set to the trial termination date if the years are the same. If the trial termination year is greater than the end year, the end day and month will be set to December 31st.

7.4. Visit Windows

Visit window will not be used in the summarization or analysis of data.

7.5. Pooling of Centres

Pooling of centers or countries will not be done. Center and country will not be included in the statistical model.

7.6. Subgroups

The analyses of the primary endpoint and selected secondary endpoints (listed below) will be repeated for the following subpopulations of the FAS:

- Age Group (≥ 85 years old vs. < 85 years old)
- Clinical Frailty Scale score (≥ 4 vs. < 4)
- History of asthma (Y/N)
- Congestive heart failure (CHF) (Y/N)
- Received a pneumococcal vaccination (Y/N)
- Received current season influenza vaccination (Y/N)
- Gender (Male vs. Female)

In each of the subgroup analyses, the independent variable relating to the subgroup will be dropped from the model, if applicable.

The selected secondary endpoints include

- (1) The percentage of subjects with CSRIs associated with ≥ 1 laboratory-confirmed pathogen(s) beginning at least 3 days after the start of study drug treatment through Week 16

This document is confidential.

- (2) The rate of CSRIs (with or without an associated laboratory-confirmed pathogen) beginning at least 3 days after the start of study drug treatment through Week 16
- (3) The rate of CSRIs associated with ≥ 1 laboratory-confirmed pathogen(s) beginning at least 3 days after the start of study drug treatment through Week 16

This document is confidential.

8. Demographic, Other Baseline Characteristics and Medication

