2.2. Timings of Analyses

The study will be unblinded after all subjects complete the final clinic visit (Week 20 visit) or terminate early from the study and the database is locked.

Analysis of the primary efficacy endpoint, including 2 subgroup analyses (specifically, for subjects who are ≥ 85 years old and subjects who have a medical history of asthma) are planned after all subjects have completed their Week 16 visit to confirm efficacy of RTB101 prior to enrolling subjects in the second Phase 3 trial (Protector 2) during the northern hemisphere winter cold and flu season. The analysis will be done when all datasets required for determination of the primary endpoint have been cleaned, frozen and changes to the required data can no longer be made. The Syneos unblinded statistical team will prepare the analysis tables and will provide them only to the resTORbio Chief Executive Officer (CEO) and Chief Medical Officer (CMO), who are not involved in the RTB-101-204 study conduct. All resTORbio personnel will remain blinded on a subject-level, and only the resTORbio CEO and CMO will be unblinded at a treatment-group level at this time.

A final analysis of other safety and efficacy and/or pharmacokinetics endpoints is planned after all subjects complete the final clinic visit (Week 20 visit) or terminate early from the study.

An independent Data Monitoring Committee (DMC) will be established. The DMC will be responsible for the following:

- Providing ongoing assessments of safety data and the overall risk of the study conduct. This will include an ongoing unblinded analysis of GI SAEs and unexpected related SAE narratives, and a monthly analysis of unblinded listings of all other SAEs.
- Advising the Sponsor of the need for study stopping or protocol modification/amendments in order to minimize potential risk for subjects.
- Advising the Sponsor if study enrollment needs to be halted based on review within 48 hours of safety data outlined in Section 5.5.5 of the protocol.

Further details are provided in the DMC charter.

This document is confidential.

3. Study Objectives

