3.6. Determination of Sample Size

Sample size was determined based on a two-sided comparison between RTB101 and placebo. In parts 1 and 2 of the Phase 2b trial, 28.2% of subjects had a clinically symptomatic respiratory illness on placebo (excluding subjects with COPD and current smokers). With an assumed Week 16 clinically symptomatic respiratory illness incidence of 28.2% on placebo and 19.7% in the RTB101 arm, a total sample size of approximately 1066 subjects (equally randomized) will provide 90% power to detect a 30% reduction in the percentage of subjects with clinically symptomatic respiratory illness between RTB101 and placebo using a two-sided test of 0.05 significance. Power analysis was conducted using Likelihood Ratio Chi-square Test.

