9.3. Primary Efficacy Endpoint Analysis

9.3.1. Primary Analysis of the Primary Endpoint

The primary efficacy endpoint is the percentage of subjects with at least one CSRI, with or without an associated laboratory-confirmed pathogen, beginning at least 3 days after the start of study drug treatment through Week 16 (H₁).

The primary efficacy endpoint will be analyzed through a logistic regression model to obtain an estimate of the population odds ratio, i.e. the odds of having a CSRI in subjects treated with RTB101 compared to the odds of having a CSRI in subjects treated with placebo and its associated confidence interval. The logistic regression model will be adjusted for factors that are known to be prognostic of outcome, specifically age (continuous covariate), clinical frailty score (ordinal covariate), medical history of diabetes mellitus type 2 (T2DM, Y/N), congestive heart failure (CHF, Y/N) asthma (Y/N), and receipt of current season influenza vaccination (Y/N). Presence or absence of asthma will be obtained from medical history records and not the stratification level entered at baseline.

Analysis of the primary efficacy endpoint will be based on the estimand for the primary objective described above.

Summary statistics will be presented along with a full data listing

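### SAP 7.6 drops age and frailty from subgroup models in which they still vary and, as a separate matter, plans no treatment-by-subgroup interaction for judging whether the effect differs

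*SAP*

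**What the plan says.** SAP 9.3.1 fits a logistic model for the primary endpoint with adjustment for baseline factors, "specifically age (continuous covariate), clinical frailty score (ordinal covariate"), plus type 2 diabetes, CHF, asthma and current-season influenza vaccination as yes/no terms.

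SAP 7.6 repeats this analysis, and three secondary analyses, within each level of seven factors. Age is split as "Age Group (≥ 85 years old vs. < 85 years old") and frailty at a score of 4. The others are asthma, CHF, pneumococcal vaccination, influenza vaccination and gender. In each subgroup model "the independent variable relating to the subgroup will be dropped from the model, if applicable".

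SAP 9.5.14 and 9.5.16 analyse the ≥85 group and the asthma group by the method of 9.3.1, with no mention of dropping a term.

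Neither document plans a treatment-by-subgroup interaction; the only interactions named are treatment by time. Neither states how a difference between levels would be judged. Protocol 9.4.4.2 leaves subgroup detail to the SAP.

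SAP 2.2 schedules the ≥85 and asthma subgroup results with the Week 16 primary analysis, whose purpose is "to confirm efficacy of RTB101 prior to enrolling subjects in the second Phase 3 trial".

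**The concern.** **Covariate rule.** A yes/no factor such as asthma is constant within its own subgroup and has to leave the model. Age is not constant across 65-84 or above 85, and frailty is not constant within scores 1-3 or from 4 upwards. The rule removes covariates that the SAP itself treats as prognostic. It also gives the ≥85 analysis two specifications: without age in 7.6, with age in 9.5.14. The SAP's index of tables has one table for the age split and no separate one for 9.5.14, so a programmer must choose.

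**No comparison between levels.** Seven factors, two levels and four endpoints give 7 × 2 × 4 = 56 separate fits and no estimate of how any two levels differ. A reader is left to set one p-value beside another. That risk is realistic here. Protocol 1.2.2 describes Phase 2b subgroups as responding or not from subgroup-specific results with nominal p-values, and Protocol 3.2 carries that reading into eligibility and into the choice of ≥85 and asthma as exploratory groups. Those two results are now to be seen before the second Phase 3 trial enrols.

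**Working it through.** **Inputs.** SAP 3.6 gives "With an assumed Week 16 clinically symptomatic respiratory illness incidence of 28.2% on placebo and 19.7% in the RTB101 arm", "using a two-sided test of 0.05 significance", and 1066 subjects 1:1 (533 per arm). Protocol 3.2 gives target-population shares of 12% aged ≥85, about 10% with asthma and about 10% with CHF, and a combined enrolment aim of at least 35% for these groups. Enrolled shares are not fixed, so the population shares are assumptions and a range is shown. Frailty, vaccination and sex shares and the size of the age effect are not in the documents and were varied.

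**1. The plan's own figure.** SAP 3.6 states that "a total sample size of approximately 1066 subjects (equally randomized) will provide 90% power" and "Power analysis was conducted using Likelihood Ratio Chi-square Test". With H(p) = p ln p + (1−p) ln(1−p), the noncentrality is 2n[H(p₁) + H(p₂) − 2H(p̄)]. At n = 533 this gives power of 90.3%. The pooled-variance normal formula

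power = Φ{(δ√n − 1.96√(2p̄q̄)) / √(p₁q₁ + p₂q₂)}, with δ = 0.085 and p̄ = 0.2395,

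also gives 90.3%. The planned size is reproduced.

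**2. Dropping age.** Take a treatment odds ratio of (0.197/0.803)/(0.282/0.718) = 0.625 and average over within-band age with SD up to 5 years. The odds ratio becomes at most 0.631 for an age odds ratio up to 2 per decade (0.640 at 3 per decade). This is a slight shift toward 1.

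**3. Unequal power under one uniform effect.** Apply 28.2% and 19.7% in every level. With f the share of the smaller level, per-arm sizes are 533f and 533(1−f). The levels share no subjects, so the chance that exactly one is significant is a(1−b) + b(1−a), where a and b are the two powers. For f = 12%: 0.201 × 0.137 + 0.863 × 0.799 = 0.717.

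| Smaller share | Power, smaller side | Power, larger side | Exactly one significant |
|---|---|---|---|
| 10% (asthma, CHF) | 17.5% | 87.1% | 74% |
| 12% (age ≥85) | 20.1% | 86.3% | 72% |
| 20% | 30.6% | 83.0% | 63% |
| 30% | 42.9% | 77.8% | 54% |
| 35% | 48.5% | 74.7% | 51% |
| 40% | 53.9% | 71.3% | 48% |
| 50% | 63.3% | 63.3% | 46% |

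SAP 2.2 names only the ≥85 and asthma groups and not their complements. Setting ≥85 beside the overall result gives a similar picture: overall significant with ≥85 not significant occurs in at least 90.3 − 20.1 = 70.2% of trials.

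**4. Do the dropped covariates cause this?** In 4,000 simulated trials per scenario (12% aged ≥85, age odds ratio 1.0 to 2.0 per decade), exactly one side was significant in 68-72% with age dropped and 69-72% with age kept. They do not.

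**5. Other ways of comparing levels.** Non-overlapping 95% CIs would occur in 0.6-1.3% of trials for shares of 10-50%. For the 10-12% groups, the smaller side would show an odds ratio above 1 in about 13-15% by calculation; simulated opposite directions were about 13-16%.

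**6. What an interaction term would do.** Its false-signal rate was 4.6-4.9% for age in simulation. Over seven unadjusted factors the chance of at least one false signal is 1 − 0.95⁷ = 30% if independent, and 27-28% simulated. For power, the variance of a level's log odds ratio is (1/n)[1/(p₁q₁) + 1/(p₂q₂)] = 11.26/n. At a 12% share the SE of the difference is √(11.26/64 + 11.26/469) = 0.447. Power for a two-fold ratio of odds ratios is Φ(0.693/0.447 − 1.96), about 34%.

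**The case against.** The strongest reply is that the SAP nowhere says levels will be compared by significance. It promises odds ratios with confidence intervals, and a reader who uses the intervals would rarely be misled (step 5). This stands. The 72% and 74% measure a likely misreading and not a planned procedure. They also assume equal placebo risk in all levels and enrolled shares equal to population shares.

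A reader might infer that dropping age and frailty makes a uniform effect look heterogeneous. The calculations do not support that (steps 2 and 4). A reader might also infer that a uniform effect would usually look different for every factor. It would not for near-even splits, which could include gender, vaccination or frailty.

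It can also be said that the phrase about applicability leaves latitude. Its natural use is for gender and pneumococcal vaccination, which are not in the model, so it does not clearly protect age or frailty.

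Finally, interaction estimates are weak and seven of them will produce false signals. That is correct. It argues for reporting them descriptively; it does not make 56 separate fits a better basis for judging differences.

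**Conclusion.** Both points hold, separately and at low to moderate severity.

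1. Dropping continuous age and ordinal frailty is unnecessary and conflicts with SAP 9.5.14. The statistical cost is a little precision and a very slight shift in the odds ratio.
2. The documents give no valid way to judge whether the effect differs between levels. If significance were used, a uniform effect would leave exactly one side significant in about 72% of trials for age ≥85 (51-74% over shares of 35% down to 10%) and about 74% for asthma or CHF, falling to 46-48% for near-even splits. The cause is unequal power.

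A reader might go further and infer that the second trial's start turns on a subgroup contrast. SAP 2.2 does not say so: it names two subgroups, no contrast and no decision rule, and gives confirmation of efficacy as the purpose. The subgroup analyses in SAP 7.6 lie outside the fixed testing sequence, so the primary conclusion is untouched.

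**What to change.** - In SAP 7.6, keep continuous age and ordinal frailty in all subgroup models, and drop only covariates that are constant within the subgroup.
- Reconcile 7.6 with 9.5.14 and 9.5.16 so that the ≥85 and asthma analyses each have one specification.
- For each factor, fit one FAS model with a treatment-by-subgroup term. For age and frailty, include the band indicator alongside the continuous or ordinal covariate. Report the ratio of odds ratios (ratio of rate ratios for the rate endpoints) with its CI beside the subgroup estimates, labelled descriptive.
- State that differences between subgroups are not inferred from separate p-values, and apply this to the Week 16 tables as well.

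The cost is SAP wording and 7 × 4 = 28 further model fits if all four endpoints are covered. No new data are needed. The downside should be stated in the SAP: about 5% false signals per factor (about 27-30% for at least one of seven on one endpoint), and power of only about 34% for a two-fold ratio of odds ratios at a 12% share. An unremarkable interaction estimate is therefore not evidence that the effect is uniform.
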